11.4 Analysis of Vital Signs and Weight

11.4.1 Variables and Criteria Defining Abnormality

The following vital sign parameters will be assessed: Systolic blood pressure [mmHg], Diastolic blood pressure [mmHg], Pulse [beats per minute], Respiratory rate [breaths per minute], Temperature [$^{\circ}\text{C}$], Weight [kg]. The following [Table 87](#) presents the Criteria for Potentially Clinically Significant Vital Sign Findings.

Table 87. Criteria for Potentially Clinically Significant Vital Sign Findings

Vital Sign	Category	Criteria for Potential Clinically Significant Vital Signs
Systolic Blood Pressure	Low Value	$\leq 90 \text{ mmHg}$ or decrease $\geq 20 \text{ mmHg}$ from Baseline
	High Value	$\geq 180 \text{ mmHg}$ or increase $\geq 20 \text{ mmHg}$ from Baseline
Diastolic Blood Pressure	Low Value	$\leq 50 \text{ mmHg}$ or decrease $\geq 15 \text{ mmHg}$ from Baseline
	High Value	$\geq 105 \text{ mmHg}$ or increase $\geq 15 \text{ mmHg}$ from Baseline
Pulse	Low Value	$\leq 50 \text{ bpm}$ or decrease $\geq 15 \text{ bpm}$ from Baseline
	High Value	$\geq 120 \text{ bpm}$ or increase $\geq 15 \text{ bpm}$ from Baseline

11.4.2 Statistical Methods

Changes from Baseline to each visit and to the final value in vital sign parameters will be summarized with the mean, standard deviation and median. The Baseline and final value means will also be presented for subjects who have both the Baseline and final values.

If there are multiple post-baseline measurements on the same day, average value will be used.

For systolic blood pressure, diastolic blood pressure and pulse, a listing of all subjects with any vital sign value meeting criteria for potentially clinically important values will be provided. For each of these subjects, the whole course of the respective parameter will be listed. The number and percentage of subjects who have at least one value meeting

criteria for potentially clinically important values will be provided for each selected vital sign parameter.

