5.3.1.1 Study Procedures

Informed Consent

The subject will sign and date a study specific, Independent Ethics Committee (IEC)/Independent Review Board (IRB) approved, informed consent form before any study specific procedures are performed in order to participate in this study. Details regarding how informed consent will be obtained and documented are provided in [Section 9.3](#).

Inclusion/Exclusion Criteria

Subjects will be evaluated to ensure they meet all inclusion criteria and have none of the exclusion criteria at both the Screening and the Week 0 visit.

Demographics

The subject's demographic data, including date of birth, gender, race, ethnicity, and disease status will be collected at the Screening Visit.

Physical Examination

Complete and targeted physical examinations will be performed at visits as described in [Appendix C](#). Complete physical examination will include general appearance as well as

evaluation of all relevant organ systems. Targeted physical examination will include vital signs assessment and evaluation of organ systems associated with AE(s) symptoms or laboratory abnormalities.

Physical examination findings that are related to subject's medical history will be captured on the appropriate medical history eCRF.

Vital Signs

Vital sign assessment includes temperature, pulse rate, sitting blood pressure, and respiratory rate, after subjects have been seated comfortably for at least 5 minutes.

Measurement of vital signs should precede blood sampling and be assessed pre-dose at all dosing visits. At Visit 2 and Visit 3 additional vital signs will be taken at 5 minutes post-dose and 60 minutes post-dose.

Subjects should be closely monitored for signs and symptoms of hypersensitivity reactions for approximately 2 hours after the first dose administered and 1 hour following all other doses of study drug. Hypersensitivity reactions should be treated according to medical standards. Pre-medications for further injections might be considered and will be agreed on between investigator and AbbVie TA MD.

Body Weight and Waist Circumference

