6.0 Analysis Conventions

Since this is an open-label continuation study, no statistical test will be conducted. Summary statistics will be provided. Data from preceding studies will be integrated with data from this study in the summaries.

Definition of Baseline

For this study, baseline values are defined as the last non-missing values prior to the first dose of study drug in this study. These baseline values will be referred to as "BL" in this document. Unless otherwise specified, this will be the "baseline" for analysis.

Definition of Rx Days (Days Relative to the Date of First Dose of Study Drug)

Rx days are calculated for each time point relative to the date of first dose of this study. They are defined as the number of days between the day of the first dose of risankizumab and the specific time point. Rx days are negative values when the time point of interest is prior to the first risankizumab dose day. Rx days are positive values when the time point of interest is on or after the first risankizumab dose day. The day of the first dose of risankizumab is defined as Rx Day 1, while the day prior to the first risankizumab dose is defined as Rx Day –1 (there is no Rx Day 0).

Definition of Analysis Windows

All time points and corresponding time windows are defined based on Rx Days.

For efficacy analyses, local tolerability, laboratory parameters, and vital sign variables, analysis windows are constructed using the following algorithm:

- Determine the nominal Rx day for each visit (e.g., Week 4 [4 weeks after Baseline visit] equals Rx Day 28).
- In order to include all post baseline data, the first post-baseline interval starts on the first day and the time after the first dose of risankizumab (Rx Day 1).
- Determine the window around a specific nominal Rx day, are presented in the Protocol Appendix C.
- If more than one assessment is included in a time window the assessment closest to the nominal day will be used. If there are two observations equidistant to the nominal day, the one after the nominal day will be used in analyses. If more than one post baseline assessment is included on the same

day, then the worst assessment on that day will be used in analyses, except those specified in Section [11.0](#).

The protocol specified visits and corresponding time windows used in the efficacy analyses, local tolerability, laboratory parameters, and vital sign variables, are presented in the following [Table 1](#) – [Table 32](#).

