Table 1. Visit Windows for Analysis of Clinical Laboratory Tests, Vital Signs, Local Tolerability (WBC, CRP and ALB), and Efficacy Variables (PASI/JDA Score and Responder Rating/PGA-GPP/CGI-GI/BSA)

Window Label	Target Day	Interval
Screening	–	[–42, –1]
Baseline ^a	1	≤ 1 ^b
Week 4	29	[2, 43]
Week 8	57	[44, 71]
Week 12	85	[72, 99]
Week 16	113	[100, 134]
Week 22	155	[135, 176]
Week 28	197	[177, 218]
Week 34	239	[219, 260]
Week 40	281	[261, 302]
Week 46	323	[303, 344]
Week 52	365	[345, 407]
Week 64	449	[408, 491]
Week 76	533	[492, 575]
Week 88	617	[576, 659]
Week 100	701	[660, 743]
Week 112	785	[744, 827]
Week 124	869	[828, 911]
Week 136	953	[912, 995]
Week 148	1037	[996, 1079]
Week 160	1121	[1080, 1142]
Week 172	1163	[1143, 1205]
Week 184	1247	[1206, 1261]
Week 188	1275	[1262, 1282]

Rx Day calculated relative to first dose of risankizumab. For subjects randomized but not dosed, Rx Day calculated relative to Randomization.

- a. There is no baseline for local tolerability measurements and CGI-GI.
- b. If time is collected, restrict to records prior to the first dose of study drug.

Table 2. Visit Windows for Analysis of Clinical Laboratory Tests (excluding WBC, CRP and ALB)

Window Label	Target Day	Interval
Screening	–	[–42, –1]
Baseline ^a	1	≤ 1 ^a
Week 8	57	[2, 85]
Week 16	113	[86, 155]
Week 28	197	[156, 239]
Week 40	281	[240, 323]
Week 52	365	[324, 533]
Week 100	701	[534, 869]
Week 148	1037	[870, 1100]
Week 172	1163	[1101, 1205]
Week 184	1247	[1206, 1261]
Week 188	1275	[1262, 1282]

Rx Day calculated relative to first dose of risankizumab. For subjects randomized but not dosed, Rx Day calculated relative to Randomization.

a. If time is collected, restrict to records prior to the first dose of study drug.

Table 32. Visit Windows for Analysis of Efficacy Variable (DLQI)

Window Label	Target Day	Interval
Baseline	1	$\leq 1^a$
Week 12	85	[2, 99]
Week 16	113	[100, 239]
Week 52	365	[240, 407]
Week 64	449	[408, 491]
Week 76	533	[492, 575]
Week 88	617	[576, 659]
Week 100	701	[660, 743]
Week 112	785	[744, 827]
Week 124	869	[828, 911]
Week 136	953	[912, 995]
Week 148	1037	[996, 1079]
Week 160	1121	[1080, 1142]
Week 172	1163	[1143, 1205]
Week 184	1247	[1206, 1261]
Week 188	1275	[1262, 1282]

Rx Day calculated relative to first dose of risakizumab. For subjects randomized but not dosed, Rx Day calculated relative to Randomization.

a. If time is collected, restrict to records prior to the first dose of study drug.

Definition of Missing Data Imputation

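### The Week 4 vital-sign summary averages pre-dose and post-dose readings, the SAP contradicts itself on Day 1 post-dose readings, and its analysis sections show no change by time after dose

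*SAP*

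**What the plan says.** **Collection.** Protocol 5.3.1.1 requires a reading before each dose: "Measurement of vital signs should precede blood sampling and be assessed pre-dose at all dosing visits". It adds: "At Visit 2 and Visit 3 additional vital signs will be taken at 5 minutes post-dose and 60 minutes post-dose". The paragraph that follows deals with acute reactions: "Subjects should be closely monitored for signs and symptoms of hypersensitivity reactions for approximately 2 hours after the first dose administered".

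**Windows.** The SAP 6.0 text says that "the first post-baseline interval starts on the first day and the time after the first dose of risankizumab (Rx Day 1"), with the stated aim of keeping all post-baseline data. Table 1 in the same section opens the first post-baseline window, Week 4, at Rx Day 2 (Days 2 to 43, target Day 29). Its Baseline row carries the note "If time is collected, restrict to records prior to the first dose of study drug". Within a window, "If more than one assessment is included in a time window the assessment closest to the nominal day will be used".

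**Same-day readings.** The general rule in SAP 6.0 is that "then the worst assessment on that day will be used in analyses, except those specified in Section" 11.0. SAP 11.4.2 sets its own rule directly after the change-from-baseline summaries: "If there are multiple post-baseline measurements on the same day, average value will be used".

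**Screen.** The next paragraph of SAP 11.4.2 lists and counts subjects with a systolic, diastolic or pulse value that meets the criteria in SAP 11.4.1. One qualifying value is enough, and the full course of that parameter is listed for each flagged subject.

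**Safety baseline.** SAP 11.1 defines it by date, so any observation dated the day of first dose qualifies. SAP 6.0 requires a value before the first dose.

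**The concern.** Readings at 5 and 60 minutes are useful for what they show relative to the reading just before the injection. A by-visit mean that pools all three hides that contrast. It also makes Week 4 a different quantity from the same row at other visits. A shift at Week 4 could reflect the time of measurement rather than time on treatment, and a short-lived change after dosing would be diluted.

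For Day 1, two programmers following the text and the table respectively would treat the same readings differently. Under the date-based safety baseline, a post-dose reading could even become the reference for every later change. Safety is a primary objective. With a minimum of 16 subjects, this schedule yields only 16 × 2 visits × 2 times = 64 post-dose readings, 32 of them on Day 1 and 32 at Visit 3.

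**Working it through.** The plan gives no figure to reproduce here, so the check follows each reading through the stated rules.

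**1. Visit 3.** Let B be baseline, p the pre-dose reading, and a and b the 5- and 60-minute readings. All three fall on the same day in the Week 4 window, so the reported change is (p + a + b)/3 − B. If p = B (an assumption made to isolate the post-dose effect), this equals [(a − B) + (b − B)]/3.

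Example with assumed systolic readings: B = 130, p = 130, a = 100, b = 130. The average is (130 + 100 + 130)/3 = 120. The reported change is 120 − 130 = −10, against 100 − 130 = −30 at 5 minutes.

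The change cut-offs in SAP 11.4.1 serve below only as a yardstick for the dilution in the by-visit summary:

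| Parameter | Cut-off c | Averaged change if one reading falls by c (−c/3) | Fall needed in one reading for the average to reach c (3c) | Fall needed in each of both post-dose readings (1.5c) |
|---|---|---|---|---|
| Systolic | 20 mmHg | −6.7 | 60 | 30 |
| Diastolic | 15 mmHg | −5.0 | 45 | 22.5 |
| Pulse | 15 bpm | −5.0 | 45 | 22.5 |

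**2. Visit 2 (Day 1), under Table 1.** If time is collected, the Baseline row takes only pre-dose records. Week 4 starts at Day 2. A Day 1 post-dose reading belongs to neither.

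**3. Visit 2, under the SAP 6.0 text.** The reading enters the first post-baseline interval, Week 4, at a distance of |1 − 29| = 28 days from target. Any reading on Days 2 to 43 is closer: at most |2 − 29| = 27 days before target and |43 − 29| = 14 days after. The Day 1 reading is therefore not selected when a Visit 3 reading exists. Extending the Week 4 window back to Day 1 would not bring these readings into the summary for such subjects.

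**4. Safety baseline.** Assume 120 before the first dose, 100 at 60 minutes on Day 1, and 102 at a later visit. From the pre-dose value the change is 102 − 120 = −18. If the date-based rule picks the 60-minute reading, it is 102 − 100 = +2.

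**5. Screen.** SAP 11.3.2 gives laboratory data a same-day rule for each analysis: average for change summaries, last value for shift tables, worst value for the grade 3 or higher listing. SAP 11.4.2 gives vital signs one rule, the average, placed after the change summaries and before the screen. It does not say whether averaging or windowing comes before the screen.

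**The case against.** A reader might infer that the post-dose readings are lost to the analysis, and that the 30 mmHg fall above would escape the 20 mmHg criterion. The documents do not support this. The screen in SAP 11.4.2 works on single values and is not tied to a visit window. The averaging sentence sits with the change summaries, and the laboratory section shows that the SAP assigns same-day rules analysis by analysis. If no special rule covers the screen, the default in SAP 6.0 is the worst value. On that reading, 100 mmHg against a baseline of 130 is flagged and the subject's course is listed.

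A reader might also infer that the Day 1 readings are simply excluded. That is one side of a conflict: Table 1 leaves them out, while the text intends to keep them.

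Nor are these the only data on acute reactions. The protocol also provides for observation after each dose, adverse event reporting of vital-sign changes (6.1.1.1) and supplemental forms for hypersensitivity (6.1.7). It states no analytic purpose for the 5- and 60-minute readings; the link to hypersensitivity is inferred from the adjacent paragraph. Finally, with about four subjects per arm in each substudy, listings tell more than means.

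All of this narrows the point. It does not alter the Week 4 mixture or the Day 1 conflict, and SAP 11.4.2 still describes no output by time after dose. The screen also does not cover temperature or respiratory rate, and its use of individual readings is implied rather than stated.

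**Conclusion.** The point holds for the by-visit summaries. Followed exactly, SAP 11.4.2 produces a Week 4 value made of one pre-dose and two post-dose readings. It cuts a change at one reading to one third and is not comparable with visits that have no scheduled post-dose readings. The one-third figure assumes that all three readings are present and that the other two equal baseline.

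For Day 1, the finding is a contradiction between the SAP 6.0 text and Table 1. Under either, the post-dose readings do not reach the by-visit summary of a subject with Visit 3 data.

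For systolic and diastolic pressure and pulse, individual abnormal readings can still be flagged on a plain reading, so the remaining gap is an unstated rule. For temperature and respiratory rate there is no such safeguard. The safety baseline in SAP 11.1 conflicts with SAP 6.0 and can take a post-dose value. The statement that no time-after-dose summary is planned rests on the analysis text in SAP Sections 6.0 and 11; the output list named as Section 17.0 could not be checked.

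**What to change.** 1. In SAP 11.4.2, use the pre-dose reading for the by-visit summaries at dosing visits.
2. State that the screen for potentially significant values uses every individual post-baseline reading, including those after dosing on Day 1.
3. Add one small table or listing of change from the same-visit pre-dose reading to 5 and 60 minutes at Visits 2 and 3, covering all vital signs, including temperature and respiratory rate.
4. Reconcile the SAP 6.0 text with Table 1 so that Day 1 post-dose readings are kept as post-baseline, for example as their own time point. Changing the text to match Table 1 as it stands would make the exclusion formal.
5. Make the safety baseline in SAP 11.1 a pre-dose value, consistent with SAP 6.0.

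The cost is minor wording and one extra output. No new readings are needed, provided the data identify which reading is pre-dose, 5-minute and 60-minute; the note to Table 1 leaves open whether time is collected.

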3.0 Introduction

Generalized pustular psoriasis (GPP) is a rare and severe skin disorder that presents with flares of widespread sterile pustules on a background of red and tender skin. It may in some cases require subject's hospitalization in intensive burn units and in rare cases be fatal.

There is no cure-all treatment for GPP, and as such, the mortality rate is high.

Erythrodermic psoriasis (EP) is a generalised erythema. It is also a very severe skin condition that can be fatal and difficult to treat. It is marked by widespread involvement (> 3/4 of the body surface area) with redness and scaling and can be accompanied by systemic manifestations such as fever, chills, or malaise. It can be the first presentation of a subject's psoriasis or can result after many years of psoriasis, sometimes as the result of a poor control of subject's existing psoriasis. Erythrodermic psoriasis should be distinguished as much as possible from cutaneous manifestation of abrupt systemic medication withdrawal or response to malignancy.

Drug Profile

[figure not shown]
For a more detailed description of the risankizumab profile please refer to the current Investigator's Brochure.

Rationale for Performing the Trial

This study will randomize from two subtypes of subjects: Generalized pustular psoriasis (GPP) and erythrodermic psoriasis (EP).

Interleukin (IL)-23 plays a key role in the pathophysiology of psoriasis through induction and maintenance of Th-17 type cells that secrete inflammatory cytokines. Risankizumab is a humanized monoclonal antibody (mAB) that specifically neutralizes the IL-23 axis. About 10% of subjects with GPP have a preceding history of psoriasis, in which there are

persistent, circumscribed, red and scaly plaques. In considering with action of mechanism of risankizumab, this medicine might be effective for GPP and EP.

therefore the aim of this trial is to obtain the efficacy, pharmacokinetic, safety, and tolerability data during a 52-week treatment period with two different dose regimens of risankizumab in Japanese subjects with GPP or EP.

The current trial is being performed to assess the safety and efficacy of risankizumab to support registration in Japan of subjects with GPP or EP.

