3.2 Benefits and Risks

Participation in this study may help to generate future benefit for larger groups of subjects with psoriasis if risankizumab proves to be successful in treating this disease. In Phase 1 and Phase 2 studies, risankizumab has been studied in approximately 200 subjects with moderate to severe plaque psoriasis. In these studies, the majority of subjects receiving risankizumab achieved 90% improvement of their disease. The most common adverse events (AE) reported in these trials were mild symptoms of the upper respiratory tract, including nasal stuffiness, sore throat, and influenza, and headache, that showed no dose dependency. These events were not considered to be related to drug treatment. Local

reactions following subcutaneous administration of risankizumab were uncommon, and limited to redness, swelling or induration at the injection site.

As with any immune modulating agent, risankizumab may impair immune function resulting in a risk of infection. This will be monitored by collection of all AEs during the treatment and observation periods. Subjects with clinically important active infection will not be included in the study. Subjects with positive QuantiFERON® tuberculosis (TB) test or a positive PPD (purified protein derivative) skin test must fulfill entry criteria as specified in Section 5.2.2, item 5, prior to receiving risankizumab. There is not enough information at this time to rule out a risk of cancer with risankizumab, but this risk is considered small with this type of compound as experience with the anti-IL-12/23 mAb ustekinumab has not suggested significant risk for cancer/serious infection. Subjects will be monitored for signs and symptoms of malignancy at each visit.

Increases in major adverse cardiovascular events (MACE) including myocardial infarction, cerebrovascular accident, and cardiovascular death, reported initially with anti-IL-12/23 agents, such as ustekinumab, have not been observed in longer term studies. While the likelihood of increased MACE is small, all suspected cardiovascular events (serious or non-serious) observed in this study will be adjudicated by an independent Cardiac, Cerebrovascular and Thrombotic Events (CCVT) Adjudication Committee.

The subjects will be administrated either 150 mg or 75 mg dose of risankizumab treatment during the clinical trial. From Week 16, subjects will be uptitrated to 150 mg if they have not achieved a clinical response.

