6.1.1 Definitions

6.1.1.1 Adverse Event

An adverse event (AE) is defined as any untoward medical occurrence in a subject or clinical investigation subject administered a pharmaceutical product and which does not necessarily have a causal relationship with this treatment. An adverse event can therefore be any unfavorable and unintended sign (including an abnormal laboratory finding), symptom, or disease temporally associated with the use of a medicinal (investigational) product, whether or not the event is considered causally related to the use of the product.

Such an event can result from use of the drug as stipulated in the protocol or labeling, as well as from accidental or intentional overdose, drug abuse, or drug withdrawal. Any worsening of a pre-existing condition or illness is considered an adverse event.

Worsening in severity of a reported adverse event should be reported as a new adverse event. Laboratory abnormalities and changes in vital signs are considered to be adverse events only if they result in discontinuation from the study, necessitate therapeutic medical intervention, and/or if the investigator considers them to be adverse events.

An elective surgery/procedure scheduled to occur during a study will not be considered an adverse event if the surgery/procedure is being performed for a pre-existing condition and the surgery/procedure has been pre planned prior to study entry. However, if the pre-existing condition deteriorates unexpectedly during the study (e.g., surgery performed earlier than planned), then the deterioration of the condition for which the elective surgery/procedure is being done will be considered an adverse event.

6.1.1.2 **Serious Adverse Events**

If an adverse event meets any of the following criteria, it is to be reported to AbbVie as a SAE within 24 hours of the site being made aware of the serious adverse event.

Death of Subject	An event that results in the death of a subject.
Life-Threatening	An event that, in the opinion of the investigator, would have resulted in immediate fatality if medical intervention had not been taken. This does not include an event that would have been fatal if it had occurred in a more severe form.
Hospitalization or Prolongation of Hospitalization	An event that results in an admission to the hospital for any length of time or prolongs the subject's hospital stay. This does not include an emergency room visit or admission to an outpatient facility.

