Appendix D. Severity Assessment Criteria Score

Severity assessment criteria score (JDA total score) specified by the Japanese Dermatological Association

A	Assessment of skin symptoms: erythema, pustules, Edema (0 – 9)		
B	Systemic symptoms/assessment of test findings: fever, WBC count, serum CRP, serum albumin (0 – 8)		
o Severity:	Mild	Moderate	Severe
(Total score)	(0 – 6)	(7 – 10)	(11 – 17)

A Assessment of skin symptoms (0 – 9)

	Severe	Moderate	Mild	None
Erythema area (total)*	3	2	1	0
Erythema area with pustules **	3	2	1	0
Edema area **	3	2	1	0

* % vs. BSA (severe: $\geq 75\%$, moderate: $\geq 25\%$ and $< 75\%$, mild: $< 25\%$)

** % vs. BSA (severe: $\geq 50\%$, moderate: $\geq 10\%$ and $< 50\%$, mild: $< 10\%$)

B Systemic symptoms/assessment of test findings (0 – 8)

Score	2	1	0
Fever ($^{\circ}\text{C}$)	≥ 38.5	≥ 37 and < 38.5	< 37
WBC count ($/\mu\text{L}$)	$\geq 15,000$	$\geq 10,000$ and $< 15,000$	$< 10,000$
Serum CRP (mg/dL)	≥ 7.0	≥ 0.3 and < 7.0	< 0.3
Serum albumin (g/dL)	< 3.0	≥ 3.0 and < 3.8	≥ 3.8

Overall Improvement Rating Defined According to JDA Total Score

JDA Total Score Change		Other Criteria	
Markedly improved	Decreased by \geq 3 points	or	No or little symptom of generalized pustular psoriasis
Moderately improved	Decreased by 1 or 2 points	or	\geq 30% reduction of erythema area with pustules compared to baseline, without reaching "no or little symptoms of generalized psoriasis" or, Clinically meaningful improvement in at least 2 of the other parameters of the severity assessment criteria (erythema area, oedema area, WBC count, CRP, fever, serum albumin) AND the sum of the changes in individual JDA components is < 3
Slightly improved	0 points (no change)	and	\geq 20% and $<$ 30% reduction of erythema area with pustules compared to baseline, or, Clinically meaningful improvement in at least 1 of the other parameters of the severity assessment criteria (erythema area, oedema area, WBC count, CRP, fever, serum albumin)
Unchanged	0 points (no change)	and	Does not fulfil the other criteria of "slight improvement"
Worsened	Increased by \geq 1 point	-	-

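### On-treatment temperature is reported only through averages and spread, with no subject-level count or listing of high values (minor, cheap to mend)

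*SAP*

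**What the plan says.** Protocol 5.3.1.1 collects the measurement: "Vital sign assessment includes temperature, pulse rate, sitting blood pressure, and respiratory rate". It also schedules extra readings 5 and 60 minutes after dosing at Visits 2 and 3.

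SAP 11.4.1 takes temperature into the safety analysis; its list of parameters includes "Pulse [beats per minute], Respiratory rate [breaths per minute], Temperature". The criteria table in that section has rows for systolic pressure, diastolic pressure and pulse only.

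SAP 11.4.2 then works at two levels:

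- **All vital signs.** Change from baseline is "summarized with the mean, standard deviation and median". Baseline and final means are added for subjects who have both. Several post-baseline readings on one day are averaged.
- **Selected vital signs.** "For systolic blood pressure, diastolic blood pressure and pulse, a listing of all subjects with any vital sign value meeting criteria" is planned, showing the full course for each such subject, with the number and percentage of subjects who meet a criterion. Temperature, respiratory rate and weight are outside this selection.

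SAP 7.1 summarises baseline temperature with minimum and maximum. SAP 11.4.2 gives neither for change on treatment.

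**The concern.** The documents tie temperature both to the drug and to the diseases. Protocol 3.2 states that "risankizumab may impair immune function resulting in a risk of infection". In GPP, fever is part of the severity score (Protocol Appendix D: "Systemic symptoms/assessment of test findings: fever, WBC count, serum CRP, serum albumin"). EP, according to Protocol 3.0, "can be accompanied by systemic manifestations such as fever, chills, or malaise".

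Within one dose-by-disease cell, temperature may therefore fall in a subject whose disease fever resolves and rise in a subject with a new fever. A mean or median pools the two. The temperature table could then look flat, or even show a fall, while a sizeable share of a very small cell is newly febrile. No planned temperature output would identify those subjects.

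**Working it through.** The plan states no figure to reproduce. The check asks what the planned statistics would show in cells of the planned size.

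**Inputs from the documents.** At least 8 subjects per disease (SAP 4.3), randomised 1:1 (Protocol 5.5.3), gives 8/2 = 4 per cell and 2 × 8 = 16 in total.

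**Assumption.** A fever raises temperature by Δ above normal, with Δ from 2.0 °C (36.6 to 38.6) to 2.5 °C (36.5 to 39.0). The documents give no rate of fever at baseline or on drug.

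**Step 1. Cells of 4.** Each row has one new fever, so a subject count would show 1/4 = 25%.

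| Changes | Mean | Median | SD (n−1) |
|---|---|---|---|
| +Δ, 0, 0, 0 | Δ/4 = 0.5 to 0.63 | 0 | Δ/2 = 1.0 to 1.25 |
| −Δ, +Δ, 0, 0 | 0 | 0 | Δ√(2/3) = 1.63 to 2.04 |
| −Δ, −Δ, +Δ, 0 | −Δ/4 = −0.5 to −0.63 | −Δ/2 = −1.0 to −1.25 | Δ√(11/12) = 1.91 to 2.39 |

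In the second row with Δ = 2.0, the baseline mean is (38.6 + 3 × 36.6)/4 = 37.1. The final mean is also 37.1, so the added means cancel in the same way.

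**Step 2. Unequal changes.** Changes of −2.0, +2.5, 0 and 0 give mean 0.5/4 = 0.125 and median 0. Cancellation is then partial but still nearly complete.

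**Step 3. Larger groups.** With one new and one resolved fever of 2.0 °C, mean and median stay at 0. The SD falls from √(8/3) = 1.63 (n = 4) to √(8/7) = 1.07 (n = 8) and √(8/15) = 0.73 (n = 16). Pooling doses or diseases weakens the one statistic that reacts.

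**Step 4. What the SD can tell.** In a cell of 4 with Δ = 2.0, one new fever alone and one resolved fever alone both give SD 1.0. The SD carries no direction, no subject and no threshold.

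**Step 5. Same-day averaging.** At Visit 3 the pre-dose reading and both post-dose readings are all post-baseline. Readings of 36.6, 36.6 and 38.6 average 111.8/3 = 37.27. A value in the top Appendix D fever band (38.5 or above) is then reported in the middle band. By contrast, SAP 11.3.2 uses the worst same-day value for significant laboratory results.

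**Step 6. Visit windows.** SAP 6.0 keeps the assessment closest to the nominal day. A fever recorded at an extra visit can therefore drop out of the by-visit summary. A count of subjects with at least one high value would keep it.

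**The case against.** A reader might infer three stronger things, and the documents support none of them.

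- **That fever is invisible in the safety plan.** Protocol 3.2 says infection risk is monitored through adverse events, and a diagnosed infection is an adverse event in its own right. Protocol 6.1.1.1 begins, "Laboratory abnormalities and changes in vital signs are considered to be adverse events only if they result in discontinuation from the study", but goes on to admit changes that need medical intervention or that the investigator considers adverse events. Adverse event tables cover both diseases, so EP is not without any fever output. White cell count and CRP have baseline-to-maximum shift tables (SAP 11.3.2).
- **That GPP fever is wholly lost in averages.** SAP 10.4 plans change in each JDA component. If these scores are treated as continuous, SAP 10.1 adds minimum and maximum, so a move between the lowest and highest fever bands would appear as +2 or −2.
- **That the SAP breaks a protocol promise.** Protocol 8.1.6 commits to mean changes, and to listings for selected parameters that it does not name. The SAP makes that selection.

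The SD also matters: mean 0 with SD 1.63 °C in four subjects does not read as an absence of change. Exact cancellation needs opposite changes at the same visit. A febrile baseline would show in the baseline minimum and maximum. Finally, SAP section 17.0, the list of outputs to be programmed, is not in the public text, so a temperature listing there cannot be excluded.

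All of this limits the point without removing it. The adverse event route depends on intervention, discontinuation or investigator judgement, so a fever put down to disease may not enter it. The JDA item is an efficacy score from 0 to 2, planned for GPP only. Neither gives a systematic count of subjects from the measured temperatures, and EP has no scored fever summary at all.

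**Conclusion.** The point holds as a minor reporting weakness. The on-treatment temperature summary alone can show 0.0 for both mean and median change, or a fall, when 1 of 4 subjects in a cell has a new fever. Its SD would signal movement without saying in which direction or in whom.

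The size rests on the assumed rise of 2.0 to 2.5 °C and on some subjects being febrile at baseline, whose frequency the documents do not give. Even with none febrile at baseline, the median misses a single new fever.

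No endpoint, population or protocol commitment is affected. The trial is descriptive, with no hypothesis tests, so the gain is a safety table that can be read subject by subject. Respiratory rate and weight are also outside the criteria, but the documents do not link them to drug risk and disease as they do fever.

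**What to change.** Before database lock, amend SAP 11.4:

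1. Add a high-value temperature row to the criteria table with a pre-specified reporting flag. The Appendix D bands at 37 and 38.5 °C are one ready choice. They grade disease severity, so they should be labelled as tabulation flags and not as a clinical rule; the sponsor may pre-specify others.
2. Add temperature to the parameters in the 11.4.2 listing (whole course) and to the number and percentage of subjects.
3. Use the highest same-day value for this count, in place of the average, and include extra visits.
4. Show baseline band against highest post-baseline band for all subjects. Restricting the count to subjects below the flag at baseline would drop someone who is febrile at baseline, recovers and then has a new fever. The shift keeps that subject in, and the listing separates persistent from new fever.

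The cost is one table row, a short change to 11.4.2 and a little extra tabulation, with no new data. The count will miss fever between visits and will include disease flares, so it should be read beside the adverse event data.
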